11.4 Plan of analysis - mechanistic studies

The analyses of the association between new ischaemic brain injury detected by MRI and each of; intraoperative air embolic load, CBF and TOI will be exploratory. Correlations between measures will be investigated, both overall and by treatment group. Comparisons of measures between treatment groups will follow the analysis plan outlined above.

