Lack of definitive evidence has resulted in a wide variability in CDI adoption in the clinical practice. Our survey has shown that surgeons are currently in equipoise, with proponents arguing for continued use of CDI, and opponents arguing that in addition to the increased costs (~£50-100 per patient), CDI may cause significant harm. In fact, CDI induces systemic hypercapnic acidosis (excess carbon dioxide causing the pH of blood and tissues to decrease), cerebral vasodilation and a relative increase in cerebral blood flow, which would counterbalance any protective effects because a higher number of microemboli (particulate or gaseous) could access the cerebral circulation (22). However, one RCT compared CDI vs. medical air insufflation in one hundred and twenty-five patients during open heart surgery and showed no

significant difference in the rate of cardiac complications experienced between the two groups (23).

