The CO2 study will assess the neuroprotective effect of CDI versus placebo (medical air insufflation) in addition to standard de-airing in patients undergoing left side heart valve surgery. In addition, the CO2 study will investigate the relationship between cerebral air embolic load and peri-operative brain injury detected by MRI and the relationship between perioperative brain injury and post-operative neurocognitive function.

4. Aims and objectives

The CO2 study aims to evaluate the efficacy and safety of CDI in patients undergoing planned open left side heart valve surgery.

It is hypothesised that in patients undergoing open heart valve surgery via partial or full sternotomy or thoracotomy, CDI plus standard de-airing is protective against ischaemic brain injury caused by cerebral embolisation (air microemboli) compared with medical air insufflation (placebo) plus standard de-airing.

Specific objectives of the trial are to evaluate:

- 1. The difference between groups receiving CDI or medical air insufflation in the incidence of acute clinical or radiographic ischemic brain injury between 2 and 10 days post procedure (primary outcome)
- The difference between groups receiving CDI or medical air insufflation with respect to a range of secondary outcomes (clinical, DWI lesion characteristics, adverse events, and patient-reported)
- The association between the burden and location with new ischemic brain lesions detected with DWI and post-operative neurocognitive function assessed by standard neurocognitive function tests

A mechanistic sub-study will also be conducted. Specific objectives of the mechanistic substudy are to determine whether there is a relationship between:

- 1. Intraoperative air embolic load detected by TCD
- 2. Cerebral blood flow (CBF) detected by TCD
- 3. Tissue oxygen index (TOI) of the frontal lobes by Near Infrared Spectroscopy (NIRS)

and ischaemic brain injury detected by MRI, and whether these relationships differ between the CDI and medical air insufflation groups.

5. Primary and secondary outcomes

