11.1.2 Mechanistic sub-study

There are no previous studies investigating the association between embolic load and brain injury post-cardiac surgery, but embolic load detected by TCD shows a strong correlation with DWI positive lesions (r=0.70) during coil embolization of unruptured intracranial aneurysms (35). Assuming a weaker association during open heart surgery the sample size for sub-study has been set at 100 participants which will provide 90% power at a 5% significance level (2-sided) to detect a correlation of 0.32 (linear regression r-squared of 0.1).

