11.3 Plan of analysis – primary and secondary outcomes

Analyses will be performed on the intention-to-treat basis and will be directed by a pre-specified statistical analysis plan. Analyses will use data from all patients randomised. Primary and secondary outcomes will be compared using logistic (binary variables), poisson (count variables), Cox proportional hazards (time to event variables), or linear mixed model (continuous variables measured at multiple time points) regression, with placebo as the reference group. Mixed models allow all participants with data to be included in the analysis, i.e. partial missing data (assumed missing at random) is permitted. Interactions between treatment and time will be examined and if significant at the 10% level, results will be reported separately for each post-operative time point; otherwise overall treatment effects will be reported. Model validity will be checked using standard methods; if a model is a poor fit, alternative models or transformations will be explored. Outcomes analysed on a logarithmic scale were transformed

back to the original scale after analysis and results presented as geometric mean ratios. Analyses will be adjusted for baseline values, and stratification variables (centre and type of surgery). Findings will be reported as effect sizes with 95% CIs.

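### Section 11.4 names no estimate of the between-arm difference in the measure–injury relationships that section 4 sets as a sub-study objective

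*Protocol*

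**What the plan says.** Section 4 gives the mechanistic sub-study two aims. The first is to find whether intraoperative air embolic load, CBF and TOI are each related to ischaemic brain injury on MRI. The second is to determine "whether these relationships differ between the CDI and medical air insufflation groups".

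Section 11.4 holds the analysis. It says that the associations of injury with "intraoperative air embolic load, CBF and TOI will be exploratory", and then: "Correlations between measures will be investigated, both overall and by treatment group". It adds one between-arm comparison: "Comparisons of measures between treatment groups will follow the analysis plan outlined above". That sentence concerns the measures themselves, not their relationship with injury. The plan it points to, section 11.3, names a single kind of interaction: "Interactions between treatment and time will be examined and if significant at the 10% level".

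Section 11.1.2 sets the sub-study at 100 participants, for 90% power at a two-sided 5% level to detect one correlation of 0.32 (r-squared 0.1). It gives no precision or power for a difference between arms.

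**The concern.** A correlation within one arm addresses whether the correlation in that arm is zero. Two such correlations side by side do not address whether the arms have the same correlation. The second aim in section 4 is therefore paired with a method that gives no estimate, interval or test for it. A reader left with by-arm results will tend to compare which of them is significant, and with about 50 patients per arm that comparison is unreliable in both directions.

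A smaller issue concerns the overall correlation. CDI is expected to lower air load and to reduce injury, and section 2.3 says that it causes "cerebral vasodilation and a relative increase in cerebral blood flow, which would counterbalance any protective effects". A correlation that pools the arms can thus carry some of the treatment effect along with the relationship of interest.

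What is at stake is the mechanistic account of how CDI works. The primary outcome, safety monitoring and the main trial's sample size are not affected.

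**Working it through.** **Inputs.** From the protocol: N = 100, r = 0.32, two-sided 5% (section 11.1.2); 1:1 allocation (section 6.5); injury 48% under placebo and a 25% relative reduction, so 0.48 × 0.75 = 36% under CDI (section 11.1.1). Assumed: 50 per arm, no missing TCD, NIRS or MRI data, and roughly bivariate normal measures unless stated.

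**1. The protocol's own figure.** With Fisher's z, power = Φ(atanh(r)·√(n − 3) − 1.96). For r = 0.32 and n = 100: 0.3316 × √97 = 3.266, and Φ(3.266 − 1.96) = 90.4%. The stated 90% reproduces.

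**2. One arm.** For n = 50: 0.3316 × √47 = 2.274, and Φ(0.314) = 62.3%.

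**3. Same true correlation in both arms, one significant and one not.** Probability = 2p(1 − p).
- Common r = 0.32: 2 × 0.623 × 0.377 = 47% (simulation of 40,000 runs: 47%)
- Common r = 0.20: 41%
- Common r = 0.40: 29% by formula, 27–28% simulated
- Common r = 0.50: 7%

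At r = 0.32 in both arms, the two sample correlations differ by more than 0.2 by chance in 27% of simulated sub-studies. A direct Fisher z test of the difference rejects in 5.0%.

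**4. The opposite error.** With true correlations of 0.70 and 0.40, both arms are significant in 83% of runs, so the by-arm tests show a contrast in only 17%. The direct test detects it in 58%.

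**5. What a direct comparison can detect.** SE of the difference in z = √(2/47) = 0.206. For 80% power the difference in z must be (1.96 + 0.842) × 0.206 = 0.578. That corresponds to 0 v tanh(0.578) = 0.52, or 0.32 v tanh(0.332 + 0.578) = 0.72. Power is 36% for 0.32 v 0, 18% for 0.32 v 0.50 and 74% for 0.32 v 0.70.

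**6. Pooling the arms.** Take binary injury at 48% v 36%, with average within-arm variance (0.2496 + 0.2304)/2 = 0.24 and total variance 0.24 + 0.12²/4 = 0.2436. Let the arms differ by d SDs on the measure. Then

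pooled r = (0.32 × √0.24 ± d × 0.12/4) / √((1 + d²/4) × 0.2436),

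with plus where the arm shift and the association point the same way.
- Load, lower under CDI, d = 0.5, 1, 2: pooled r = 0.34, 0.34, 0.31, against 0.32 within arm.
- CBF, higher under CDI with a positive association with injury, d = 0.5, 1, 1.5: pooled r = 0.28, 0.23, 0.18. Simulated power is 81%, 64% and 43%, against 91% adjusted for arm. At d = 0.2 it is 88%.
- No within-arm association: pooled r is 0.03, 0.05 and 0.09 at d = 0.5, 1 and 2, and cannot exceed √(0.0036/0.2436) = 0.12.

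The protocol gives no value for d, so every shift here is an assumption.

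**The case against.** The strongest reply is that section 11.4 does not commit the trial to anything faulty. It labels the analyses exploratory, and it sets no threshold or decision rule for a between-arm difference. Correlations by group are a usual first step and exclude neither an interaction term nor a comparison of correlations. Sections 6.2 and 11.3 promise a detailed analysis plan, which is not at hand and may contain one. All of this stands. A reader might infer that the trial will declare a difference whenever one arm is significant and the other is not. The protocol does not say so, and the 47% is the risk of that misreading, not the error rate of a stated rule.

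A reader might also infer that the overall correlation is unadjusted and materially distorted. Section 11.4 is silent on adjustment. For embolic load, the measure that section 11.1.2 uses to justify the sample size, pooling changes little. Part of the between-arm variation in load may also be the causal path of interest, so whether to remove it is a choice of estimand. The CBF attenuation needs a sizeable shift, and the control of PaCO2 described in section 7.1.2 may limit it during bypass.

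What remains is that the objective is explicit, a method for these relationships is named, and that method yields no estimate of the contrast. An exploratory label lowers the weight of an answer but does not make the method address a different question.

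**Conclusion.** The point holds in a limited form. The second sub-study aim in section 4 has no matching estimate in section 11.4, and by-arm correlations would mislead if read as one. The risk is about 47% when both arms share the design correlation of 0.32, and 41% to 7% for common correlations of 0.20 to 0.50. These figures rest on 50 per arm, complete data and near-normal measures. With binary injury the discordance at 0.32 is still 47% by simulation, against 4.3% for a direct test.

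The pooling issue is secondary: negligible for load, and possible attenuation for CBF if CDI raises it materially. It supports reporting an adjusted association but does not show the pooled correlation to be wrong.

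Severity is minor, because this is an optional, single-centre, exploratory sub-study.

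**What to change.** In section 11.4, add after the sentence on correlations:

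> For each measure, MRI injury will be regressed on the measure, treatment group and their interaction (logistic regression where injury is lesion present or absent). The interaction estimate with its 95% CI is the exploratory answer to the between-group objective. Within-group correlations are descriptive. The treatment-adjusted overall association will be reported beside the pooled correlation.

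In section 11.1.2, add that 100 participants were set for one overall correlation. At about 50 per group, a difference has 80% power only for correlations of about 0 v 0.52 or 0.32 v 0.72, so a non-significant interaction does not show that the relationships are the same. These figures come from comparing correlations. An interaction compares slopes, so they are a guide to its power rather than an exact statement.

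The cost is one extra model per measure and a short paragraph, with no new patients or data. The downside is a comparison that is openly imprecise and will often leave the objective unanswered. If the SAP already names such an interaction, a cross-reference from section 11.4 is enough.

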11.5 Frequency of analyses

The primary analysis will take place when follow-up is complete for all recruited patients. The value of including an interim will be discussed with the DMSC. Safety data will be reported to the DMSC approximately every six months, together with any additional analyses the committee request.

11.6 Criteria for the termination of the trial

The trial may be terminated early by the TSC. A decision to terminate may arise from a recommendation by the DMSC to stop the trial, for example based on *an interim analysis of the data from the trial* or if the results of another study make the completion of the trial unnecessary.

12. Trial management

University Hospitals Bristol and Weston NHS Foundation Trust will act as Sponsor. Responsibility for running the CO2 study will be established via a collaboration agreement with the University of Bristol. Agreements between the Sponsor and participating centres will be required, as well as standard site initiation documents, before recruitment commences. The study will be conducted in accordance with GCP guidelines, the European Union Directive 2001/20/EC on clinical trials, the Data Protection Act and the UK Policy Framework for Health and Social Care Research. The trial will be registered on an open access clinical trial database (ISRCTN). Clinical trial documents will be archived and held by the Sponsor for 15 years after study closure in accordance with the standard operating procedures of the Sponsor and in compliance with the principles of GCP.

The study will be managed by the Chief Investigator (CI), with mentoring and support from senior members of the research team who will provide experience of implementing large scale clinical trials, and the Trial Manager, with full support from the wider BTC CTEU, which is a UK Clinical Research Collaboration registered clinical trial unit (UKCRC Reg. No 11). The BTC CTEU has an established track record of designing, conducting, managing and reporting multicentre clinical trials. The BTC CTEU has experience in building study database systems and providing randomisation services.

The CI and BTC CTEU team will work with the co-applicants to prepare the final protocol and submit the REC, MHRA and associated HRA applications. The BTC CTEU will prepare the study manual, provide the randomisation service and design and implement the data management system.

The CI, BTC CTEU team and Sponsor will endeavour to ensure that the trial runs according to the agreed timetable, recruitment targets are met, the CRFs are completed accurately, the trial complies with relevant ethical and other regulatory standards, and that all aspects of the study are performed to the highest quality. The CI and BTC CTEU team will also train investigators at participating centres, check that centre are ready to start ("green light") and monitor their progress during the study. The Trial Manager will be the contact point to provide support and guidance to the participating centres throughout the study.

12.1 Day-to-day management

The CO2 study will be managed by a Trial Management Group (TMG), which will meet face-to-face or by teleconference approximately monthly. The TMG will be chaired by the Chief Investigator and members of the named research team will be invited as appropriate (see Chief Investigator & Research Team Contact Details).

An appropriately qualified person by training will be responsible at each site for identifying potential trial participants, seeking informed participant consent, randomising participants, liaising with pharmacy, collecting trial data and ensuring the trial protocol is adhered to.

12.2 Monitoring of sites

12.2.1 Initiation visit

Before the study commences, training session(s) will be organised by the BTC CTEU. These sessions will ensure that personnel at each site involved fully understand the protocol, CRFs, the operational requirements of the study and the assessments to be conducted within the trial e.g. neurocognitive function tests.

12.2.2 Site monitoring

The trial coordinating centre will carry out regular monitoring and audit of compliance of centres with GCP and data collection procedures described in section 7.3. Monitoring of data collection will be via the study database (checks for data completeness and routine data query review), which will be carried out on a regular basis. The Investigator Site File and CRFs will be monitored by site self-completed checklists at least once in the lifecycle of the trial. The TMG will review accumulating data on, including but not limited to, screening, eligibility, recruitment, data completeness, adherence to trial visits and procedures, adverse events and protocol deviations in the form of central monitoring reports generated approximately monthly.

12.3 Trial Steering Committee and Data Monitoring and Safety Committee

An independent TSC will be established to oversee the conduct of the study. It is anticipated that the TSC will comprise the CI, an independent chair and at least two additional independent members, at least one of whom will be a patient/public representative. The TSC will develop terms of reference outlining their responsibilities and operational details. The TSC will meet before recruitment in the trial begins and then approximately every six months during the course of the study.

An independent DMSC will be established to review safety data during the course of the study and will advise on interim analyses. The DMSC will develop a charter outlining their responsibilities and operational details. The DMSC will meet jointly with the TSC, before recruitment in the trial begins and they will meet approximately every six months after recruitment has begun.

Stopping rules for the trial will be discussed at the first joint TSC/DMSC meeting, and decisions documented in the DMSC Charter.

13. Ethical considerations

13.1 Review by an NHS Research Ethics Committee

The research will be performed subject to a favourable opinion from an NHS REC and Health Research Authority (HRA) approval, including any provisions of a non-NHS site assessment form. Ethics review of the protocol for the trial and other trial related essential documents (e.g. PIL and consent form) will be carried out by a UK NHS REC. Any subsequent amendments to these documents will be submitted to the REC and HRA for approval prior to implementation.

13.2 Risks and anticipated benefits

The conduct of this study will allow us to determine which of the treatments is the most clinically effective, as such, this study will allow us to make evidence-based recommendations for the treatment of this patient population.

There are no known risks or benefits in either intervention in this trial population; this will be quantified as part of this study.

13.3 Informing potential study participants of possible benefits and known risks

Information about possible benefits and risks of participation will be described in the PIL.

13.4 Obtaining informed consent from participants

All participants will be required to give written informed consent. This process, including the information about the trial given to patients in advance of recruitment, is described above in section 10.3.

The PI or members of the team delegated by the PI will be responsible for obtaining informed consent. The consent process will be described in detail in the study manual. Research personnel authorised to obtain consent will be recorded on the Delegation of Responsibilities Log. All individuals obtaining informed consent will have received GCP training.

13.5 Co-enrolment

Subject to agreement with the Chief Investigator, a participant may be co-enrolled to a non-intervention study as well as to the CO2 study. A participant must not be co-enrolled to another intervention study while they are actively participating (up to the three-month follow up visit) in the CO2 study.

14. Research governance

This study will be conducted in accordance with:

- The Medicine for Human Use (Clinical Trial) Regulations 2004
- Good Clinical Practice (GCP) guidelines
- UK Policy Framework for Health and Social Care Research

14.1 Sponsor approval

Any amendments to the trial documents must be approved by the sponsor prior to submission to the HRA, REC and MHRA as applicable.

14.2 NHS confirmation of capacity and capability

Confirmation of capacity and capability is required from each participating site prior to their participation in the trial.

Any amendments to the trial documents approved by the REC, HRA and MHRA (if applicable) will be submitted to participating sites for information and implementation, as required.

14.3 Investigators' responsibilities

Investigators will be required to ensure that local research approvals have been obtained and that any contractual agreements required have been signed off by all parties before recruiting any participant. Investigators will be required to ensure compliance to the protocol and study manual and with completion of the CRFs. Investigators will be required to allow access to study documentation or source data on request for monitoring visits and audits performed by the Sponsor or the BTC CTEU or any regulatory authorities.

Investigators will be required to read, acknowledge and inform their trial team of any amendments to the trial documents approved by the REC that they receive and ensure that the changes are complied with.

14.4 Monitoring by sponsor

The study will be monitored and audited in accordance with University Hospitals Bristol and Weston's Monitoring and Oversight of Research Activity SOP, which is consistent with the UK Policy Framework for Health and Social Care Research and the Medicines for Human Use (Clinical Trials) Regulations 2004. All study related documents will be made available on request for monitoring and audit by the sponsor (or the BTC CTEU if they have been delegated to monitor see 7.2.2), the relevant REC and for inspection by the MHRA or other licensing bodies. A monitoring plan will be prepared by the Sponsor.

14.5 Indemnity

This is an NHS-sponsored research study. For NHS sponsored research if there is negligent harm during the clinical trial when the NHS body owes a duty of care to the person harmed, NHS Indemnity covers NHS staff, medical academic staff with honorary contracts, and those conducting the trial. NHS Indemnity does not offer no-fault compensation and is unable to agree in advance to pay compensation for non-negligent harm. Ex-gratia payments may be considered in the case of a claim.

